## Purpose of the Study

This is an observational, direct-to-participant sub-study that distributes at-home, self-administered, SARS-CoV-2 antigen testing kits to people in designated communities. Duke will be in charge of the coordination of the sub-study. Adults and children living within the pre-identified communities will be invited to take part in the substudy, provided they meet the inclusion criteria. Potential subjects will self-identify by actively choosing to seek further information about the study via REDCap or by calling the DCRI Call Center. They will be able to participate via REDCap or through the DCRI Call Center. The study will be called You & Me COVID-Free Research Study.

## Background & Significance

In the US, > 4 million people have been infected with the SARS-CoV-2 virus and >400,000 died. Infections and deaths, however, have disproportionately affected historically marginalized populations. Early in the pandemic the focus has been on testing to identify symptomatic individuals to reduce morbidity and mortality from infection. As public health measures have scaled up mitigation strategies are increasingly being considered to reduce community spread of infection. The availability of rapid tests for detecting SARS-CoV-2 presents opportunities for rapid, frequent and low-cost at-home testing in asymptomatic populations as part of a broader mitigation strategy that includes protective measures (masking, social distancing, increased hygiene) and contact-tracing and isolation. With 50% or more of infections resulting from pre-symptomatic or asymptomatic transmission, at-home testing may offer an effective option for screening and for breaking chains of transmission. Rapid antigen tests are relatively inexpensive and therefore can be used frequently for detecting infected individuals who are asymptomatic, pre-symptomatic and without known or suspected exposure to SARS-CoV-2. However, even with antigen tests, the implementation of community level testing will be challenging, with an impact that is still to be determined.

The public health crisis of the COVID-19 pandemic continues to rage on across the US. Novel mitigation strategies and community level public health interventions are critical to stop the spread of this virus. One of these interventions is frequent, low-cost, rapid-result, at-home viral screening of asymptomatic and symptomatic individuals. The goal of frequent home testing is to identify SARS-CoV-2 index cases early, trigger isolation and quarantining precautions, and ultimately decrease community transmission. The Centers for Disease Control, through coordination with public health departments, is conducting a public health intervention of frequent home testing, completed in a timeline needed to address the pressing need in high-risk communities. This intervention of home testing requires intentional engagement and a clear recognition of risk. Within pre-selected communities, CDC will distribute at-home, self-collect/self-testSARS-CoV-2 tests with instructions to complete regular testing irrespective of symptoms or exposure history. Previous at-home testing studies have generated inconclusive results, in part due to multiple factors including inadequate community engagement strategies to promote uptake and consistent testing in the target population as well as limited testing and prevention knowledge, attitudes and behavior. This cohort sub-study in a subset of the population will explore the community and human behavior factors in response to at-home testing. Participants in the public health intervention who meet eligibility criteria will be invited to participate in the sub-study, consented, and asked to complete questionnaires aimed at evaluating self-reported social interactions, behaviors, and

health system utilization in response to results from the at-home SARS CoV-2 antigen test. This sub-study will provide participant level behavioral information essential to understanding the relationship between large scale at-home testing and community transmission during the SARS-CoV-2 pandemic and relevant for implementation of public health interventions in future pandemics.

### Design & Procedures

This is an observational, direct-to-participant sub-study that distributes at-home, self-administered, SARS-CoV-2 antigen testing kits to people in designated communities. This sub-study focuses on gathering participant-level data to evaluate behavioural determinants of home testing and socio-behavioural mechanisms of SARS-CoV-2 community transmission. As part of the public health intervention, households will receive test kits and included in them will be information about the REDCap surveys and a QR code to facilitate access. Only after the participants have received the testing kits, will they be offered the option to participate in this sub-study. Once registered, if the participant wants to be a part of the sub-study, eligibility criteria will be verified and consent will be obtained through REDCap. Push notifications will be programmed using Twilio for adherence to taking surveys. For participants who provide consent to the sub-study, the app will also feature the ability to report the results of their test results, and respond to surveys and questionnaires. As an alternative to REDCap, participants can participate in the study via phone interviews conducted by a centralized study call center. Home test kits will include a QR code for the REDCap surveys and a toll-free number to the DCRI call center/eConsent for those interested in participating. Using scripted interview guides, call center staff will be ready to explain study participation, obtain verbal consent, administer study questionnaires including soliciting test results, and issue phone reminders for participants who chose not to use REDCap. Using NIH Tier-1 Common Data Element (CDE) measures, the surveys and questionnaires will collect data on demographic characteristics, medical history and health status, SARS-CoV-2 testing and symptoms, social interactions, knowledge of prevention strategies, and infection risk, and attitudes towards vaccines.

Participants will be asked to complete a front-door questionnaire to determine interest in completing the study. After completing the swab test, they are asked to take a baseline survey (20 minutes to complete), then 28 days later they are prompted via text and email to take the end-of-study survey (about 1 minute to complete).

### Selection of Subjects

In order to be eligible to participate in this study, an individual must sign and date informed consent form. There are no exclusion criterias if inclusion are met. Community selected is Merced County, CA.

### Subject Recruitment and Compensation

Through partnership with CCPH, the United Way of Merced County, CA was identified as the lead Community Partner to spearhead the enrollment of this substudy. Using materials created by the study team, they will introduce to study subjects in their region. They hope to enroll approximately 100,000 subjects by providing free COVID-19 test kits, and asking participants if they will answer questions in a

survey for a chance to receive a gift card. If participants would like to answer survey questions, they will follow a QR code to access REDCap and will be guided through the eConsent process. Participants may be compensated via Amazon gift card (up to \$60) as detailed in the consent form.

If a participant is interested in the sub study, they will either call the DCRI call center to verbally consent or will click a link to access REDCap. If they would like to learn more, they will be taken to the consent form, will fill that out and then will complete surveys. If they have questions either through REDCap or website about the sub study, they will be directed to call the DCRI call center to have their questions answered. The compensation schedule is listed in the consent forms as follows:

If the participant chooses to be part of our study, they will be asked to complete survey questions, and will complete surveys after testing. Combined, the three surveys (1 short survey, 1 detailed survey, and, 28 days later, 1 final short survey) will take about 20 minutes to complete:

For pre-consent survey: Participant has a 1 in 10 chance of receiving a \$10 gift

For post-consent surveys: Participant will be provided gift cards worth up to fifty dollars, and will be paid according to the following schedule:

\$25 after you complete Survey 1

\$25 after you complete Survey 2

There is no travel time or lost wages incurred as there are no study visits.

Participants will have access to the You and Me COVID-free website, <https://youandmecovidfree.org/>.

#### Risk/Benefit Assessment

Study-related risks include potential loss of confidentiality but steps will be undertaken to minimize this risk. There are no interventions involved in this study. The benefit of this study is to learn testing impact on reducing the community spread of the infection, however there is no direct benefit to participants.

#### Data Analysis & Statistical Considerations

The approach to analysis will be primarily descriptive. Demographics, questionnaire data, and testing results will be reviewed and summarized using graphical techniques and summary statistics. Where applicable, exact method confidence intervals will be computed around point estimates. Trends over time will be evaluated graphically. The proportion of participants adhering to social distancing guidelines after a positive vs. negative test result will be compared using tests of proportion clustered by participants with various levels of intra-participant correlation. Stratified analyses by test or week number will also be performed. We will explore the associations between positive test results and critical behavioral measures using mixed modeling techniques to account for the participant and household correlations. Analyses will be conducted using SAS (SAS Institute, Cary NC) and R with R Studio (R-project). Point estimates with 95% confidence intervals will be reported. The analysis will be done for applicable study populations as described above, and stratified by participant demographics of

interest (e.g., age, gender). There will be a comparison of the proportion of participants that report adhering to social distancing guidelines after positive vs. negative test result.

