This cohort sub-study in a subset of the population will explore human factors in response to testing and vaccination. Participants in the public health intervention who meet eligibility criteria will be invited to participate in the sub-study, consented, and asked to complete questionnaires aimed at evaluating self-reported health conditions, COVID-19 testing and symptoms, social interactions, knowledge of prevention strategies, infection risk, and attitudes towards vaccines. This sub-study will provide participant-level information essential to understand COVID-19 testing and vaccination awareness and access and relevant for implementation of public health interventions in future pandemics.

Further details of the background and the design of the study can be found in the study proposal.

Specific Analysis Aims

1. Characterize self-reported COVID-19 testing and symptoms.
2. Delineate attitudes towards SARS CoV-2 vaccination.
3. Describe infection risk in work place.
4. Explore the relationship between sociodemographic factors, i.e., age, race, ethnicity, and preferred language, and
 - a. reasons for test use,
 - b. test result,
 - c. current vaccination status,
 - d. likelihood of future vaccination,
 - e. perspective on easiest way to obtain free oral COVID medicines.
5. Explore the relationship between social determinants of health, i.e., gender identity, employment, food/water/housing insecurity, health insurance, and COVID-19 challenges, and
 - a. testing attitude (i.e., Participant thinks it is easy to get tested for COVID-19)
 - b. testing behavior (i.e., Participant has been tested for COVID-19)

Study Population

The study population will consist of people who meet the following criteria:

- Adult and child residents who are 2 years of age or greater at enrollment
- Self-report primarily residing within the intervention community (Merced County, California)
- Are participating in the public health intervention, regardless of vaccination status

The questionnaire includes three parts:

- Front Door Survey
- Baseline Survey
- End of Study Survey

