The Front Door Survey and the Baseline/End of Study Surveys cannot be linked due to the way they were set up, despite the fact that there are matching record IDs. Each entry in the Front Door Survey corresponds to a unique test result. Multiple test results can correspond to the same participant, but each test result receives a unique record ID so there is no way to link the multiple results to one participant. Each participant can sign up once to take the Baseline Survey and End of Study Survey, and each unique record ID represents one participant in the Baseline and End of Study Surveys. An observation from the Baseline and End of Study Surveys will have the same record ID as an observation in the Front Door Survey. However, this does not necessarily mean that the information across both sets of surveys are from the same participant. In order to clarify the data flow of the YMCF project, the consort diagram in Figure 1 presents data from the Front Door Survey on the number of total entries, the number of valid test results, and completeness of the primary outcomes. It also presents data from the Baseline Survey on the and number of total participants, the number of consented participants, and completeness on secondary outcomes. The primary outcomes correspond to the Front Door Survey and are:

- Participant reasons for test use
- Test result
- Current vaccination status

- Likelihood of future vaccination
- Perspective on easiest way to obtain free oral COVID medicines

Among 2,399 valid-test-result entries in Front Door Survey, 412 entries completed full set of primary outcomes, 1,987 entries partially completed primary outcomes, and none entry were missing all primary outcomes. See details in Table 1.

Table 1. Missingness of Primary Outcomes in Front Door Survey

	Participant reasons for test use	Test result	Current vaccination status	Likelihood of future vaccination	Perspective on easiest way to obtain free oral COVID medicines
Missing	0	0	4	1987	0
Not missing	2399	2399	2395	412	2399
Total	2399	2399	2399	2399	2399

The secondary outcomes correspond to the Baseline Survey and are:

- Participant attitudes towards SARS-CoV-2 vaccination
- Accessibility to personal protective equipment and distancing in the work place
- Self-report COVID-19 testing and symptoms

[figure not shown]

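### Does the SAP need to withdraw formally the protocol's comparison of distancing after a positive versus a negative test, now that the survey records cannot be linked?

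*Protocol*

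**What the plan says.** The protocol's Data Analysis & Statistical Considerations section calls the approach mainly descriptive and then names several comparisons. The proportion keeping to distancing guidance "after a positive vs. negative test result will be compared using tests of proportion clustered by participants with various levels of intra-participant correlation". The section repeats this at its end: "There will be a comparison of the proportion of participants that report adhering to social distancing guidelines after positive vs. negative test result". It adds "Stratified analyses by test or week number will also be performed", and proposes to explore positive results against behavior with "mixed modeling techniques to account for the participant and household correlations". Background & Significance gives the matching purpose: questionnaires on social interactions, behaviors and "health system utilization in response to results from the at-home SARS CoV-2 antigen test".

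The SAP's Background restates that purpose as "questionnaires aimed at evaluating self-reported health conditions, COVID-19 testing and symptoms, social interactions, knowledge of prevention strategies, infection risk, and attitudes towards vaccines", with no mention of response to a result. Its Study Population section explains why: "The Front Door Survey and the Baseline/End of Study Surveys cannot be linked due to the way they were set up". Within the Front Door Survey, "each test result receives a unique record ID so there is no way to link the multiple results to one participant". The same section warns that a record ID shared across surveys may not denote one person, and it confines all analyses to the Front Door and Baseline evaluable populations. Under Objective 5 the SAP concedes that unrecognized repeat entries may make its standard errors too small.

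**The concern.** Read side by side, the two documents do not meet. The protocol commits twice to a comparison that goes to the heart of the sub-study's stated purpose. The SAP describes a data structure in which that comparison cannot be made for the kit result, then moves to other objectives without saying what became of it. The change history for version 2.0 mentions only a revision in response to comments.

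If that silence misled anyone, two things would be at stake. A reader of the eventual report might wonder whether the comparison was impossible or was run and left out. And because record IDs do coincide across surveys, an analyst might be tempted to merge on them and produce a spurious analysis of behavior after a test.

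**Working it through.** Neither document gives a sample size, power or effect size for these analyses, so there is no planned figure to reproduce. The check sets each commitment against what the SAP shows.

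**1. What each analysis needs, for the kit result**

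| Protocol analysis | Needs | SAP shows | Status |
|---|---|---|---|
| Distancing by result, clustered by participant | Result and behavior on one person's record; a participant ID or an assumed correlation | Result on the Front Door Survey; no link to the other surveys | Cannot be run with verified links |
| Stratification by test number | Order of each person's tests | Repeat results cannot be grouped | Cannot be run |
| Stratification by week number | An entry date | Nothing said to prevent it | Omitted, not shown to be blocked |
| Mixed model, participant effect | Participant ID and behavior | Neither available with the result | Cannot be run |
| Mixed model, household effect | Household ID and behavior | No household ID described | Missing ID inferred from silence; behavior link still absent |

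The protocol offers test number or week number as alternatives, so the stratification as a whole is not shown to be impossible.

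**2. Counts**

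- Valid Front Door results: 2,510 − 111 = 2,399, matching the SAP's figure and its missingness split (412 + 1,987 = 2,399).
- Results verifiably linked to a Baseline or End of Study record: 0 of 2,399.
- Front Door variables named in the SAP: 8 in Appendix Table 5 (age category, race, ethnicity, reason for testing, result, vaccine dose, likelihood of vaccination, easiest source of oral medicine) + 1 in Objective 5 (preferred language) = 9. Those measuring distancing or other behavior after a result: 0. Table 5 is not stated to be the full item list.
- SAP objectives and tables that contain the distancing comparison or a mixed model: 0 of 6 and 0 of 7.

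**3. What is not blocked**

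The protocol speaks of a test result, not specifically the kit entry. The Baseline Survey has its own: Appendix Table 2 lists ever testing positive and the result of the most recent test. It is given straight after the Front Door Survey, so the most recent result may often be the kit result, though this cannot be verified. Each record ID denotes one participant across the Baseline and End of Study Surveys, so those two do link. If a distancing item was collected, a comparison with one record per person remains possible. The questionnaires are not in the documents, so this cannot be settled.

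**4. What a withdrawal statement would alter**

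Each SAP objective draws on one survey only, so no planned table merges them and no estimate depends on the failed link. The lost participant ID matters in one planned place, the Front Door regressions in Objective 5. As an illustration, take a factor constant within a person and equal cluster sizes. The true two-sided error at nominal 0.05 is then 2 × [1 − Φ(1.96/√D)], with D = 1 + (m − 1) × ICC. Assuming m = 2 entries per person:

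- ICC 0.1: D = 1.1, error 0.062
- ICC 0.8: D = 1.8, error 0.144

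The values of m and ICC are assumptions. The SAP already names this inflation, and announcing that other analyses are dropped would not reduce it.

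**The case for a change.** The strongest case for a change is that disclosing a data limit is not the same as saying which promised analyses it ends. The SAP spells out the consequence only for the standard errors in Objective 5. It was also written with observed counts and missingness in hand, which is when a reader most wants an explicit reason for a narrower analysis set. A sentence of withdrawal and a rule against merging would cost almost nothing. End of Study data raise a similar question: participants are paid for that survey, yet no objective or table uses it.

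Part of this stands. No sentence withdraws the protocol analyses, and the protocol's purpose statement has not been brought into line with the SAP's.

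The rest is weaker. For the kit result, a reader can tell impossibility from selective reporting, because the SAP says plainly that the surveys cannot be joined and that repeat results cannot be traced to one person. A rule against merging would repeat the SAP's own warning about record IDs. The SAP's limit to the Front Door and Baseline populations already answers the End of Study question. A blanket withdrawal would also go further than the documents support: it would cover week-number stratification and household models that are not shown to be impossible, and might close off the Baseline route without examining it.

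**Conclusion.** The mismatch is real, but it is a documentation gap that calls for no change to the plan. The SAP has in effect dropped the analyses that depend on the missing links, and it gives the reason. The size is 0 verifiable links among 2,399 kit results before any rewording and 0 after it, with no estimate, interval or test in the 7 planned tables affected. A line in the study report, noting that the protocol's comparison by kit result could not be made and why, is what a sensible analyst would write anyway.

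This rests on three assumptions: that analysts heed the warning about record IDs and do not merge the surveys; that the Front Door items named in the SAP fairly represent that survey; and that no report claims a behavioral response to the kit result. If such a claim appeared, the missing link would become a substantive objection to it.
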